1.2 Purpose

The purpose of the study is to determine the safety and efficacy of topical ocular ECF843 compared to topical ocular vehicle (Part 1) for the relief of the signs and symptoms associated with moderate to severe DED. The study design includes a component for dose-regimen selection. Part 2 of the study is intended to explore additional endpoints and potential areas of differentiation as a treatment for patients with DED.

This Phase II study will establish the foundation for further development and registration of ECF843.

2 **Objectives, endpoints and estimands**

Table 2-1Objectives and related endpoints

Objective(s)	Endpoint(s)	
Primary objective(s)	Endpoint(s) for primary objective(s)	
• Part 1: To demonstrate superiority of ECF843 versus vehicle for improvement in dry eye related ocular symptoms and ocular surface damage	 Change from baseline in Symptom Assessment in Dry Eye (SANDE) score; 	
	Change from baseline in composite corneal fluorescein staining score	
Secondary objective(s)	Endpoint(s) for secondary objective(s)	
 Part 1: To evaluate the improvement of ECF843 vs vehicle in corneal damage by quadrant 	Change from baseline in inferior and central corneal fluorescein staining	
• Part 1: To evaluate the safety of ECF843 vs Vehicle	 Incidence and severity of ocular and non-ocular adverse events 	

2.1 **Primary Estimands**

The estimand is the precise description of the treatment effect and reflects strategies to address events occurring during trial conduct which could impact the interpretation of the trial results (e.g premature discontinuation of treatment).

The primary clinical question of interest is: What is the treatment effect of ECF843 versus vehicle on change from baseline in signs and symptoms in subjects with moderate to severe DED, if artificial tears/gels/lubricants and prohibited medications were not used, and treatment was received for the entire study duration?

The justification for the primary estimands is that they will capture the effect of the study drug for the full duration when administered without confounding effects from prohibited medications or artificial tears/gels/lubricants. Further details can be found in Section 12.

The primary estimands are described by the following attributes:

- 1. Population: subjects with moderate to severe DED. Further details about the population are provided in Section 5.

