4.1 Rationale for study design

Part 1 of the study is a double-masked, randomized, parallel design which includes two concentrations and two posologies in order to evaluate the difference in efficacy based on concentration and frequency of dosing. Because administration of vehicle does provide benefit to subjects and shows some efficacy in many dry eye clinical studies, there is not a true placebo (e.g., a treatment that has no effect on the disease being studied). Therefore, it is important to compare active to vehicle at the same frequency of dosing. To address this, there are two vehicle arms: one for comparison of BID active vs vehicle and one for TID active vs vehicle.

The primary objectives for Part 1 of the study are based on the assessment of ocular symptoms (via an at home daily electronic diary using the SANDE VAS symptom scores) and ocular surface damage assessed by the degree of corneal fluorescein staining. These are well established endpoints that are recognized as key parameters to define severity of the dry eye disease state, as well as improvement in the disease severity after treatment.

The active and vehicle test articles are presented in identical packaging to ensure no bias to the study results due to knowledge of the treatment assignment. There is an additional level of masking which includes the selection of subjects that will be included in the primary efficacy analysis of the study. The criteria for selection of these subjects is pre-defined and documented in the statistical analysis plan (SAP) but is not disclosed to the Investigator nor the subject to avoid the selection bias and regression effects that have been observed in many historical dry eye studies. The criteria for selection of subjects into the primary analysis are within the guidelines of the stated entry criteria for the study in order to protect against any unintended risk to the subject. In order to preserve this level of masking, and to allow for exploration of differences in treatment outcomes between the population of subjects who are selected vs those that are not, all subjects will remain in the study for the full treatment period.

Part 2

Part 2 of the study is an exploratory, double-masked, randomized parallel assessment of ECF843 vs Vehicle.

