5.2 Exclusion criteria

Subjects meeting any of the following exclusion criteria at the Screening Visit in Part 1 are not eligible for participation in the study.

Subjects meeting any of the following exclusion criteria at the Screening and Baseline Visits in Part 2 are not eligible for participation in Part 2 of the study.

- 1. Ocular infection (bacterial, viral, or fungal) in either eye within 30 days prior to Screening
- 2. Use of artificial tears, gels, lubricants within 4 hours of conducting assessments at the Screening Visit
- 3. Use of contact lenses in either eye within 14 days of Screening, and any use of contact lenses for the duration of the study
- 4. Subjects with **uncontrolled** ocular rosacea (affecting the eye adnexa), posterior blepharitis or Meibomian gland dysfunction

NOTE: Controlled is defined as a stable condition, not as an asymptomatic condition. If the subject is doing lid scrubs and/or warm compresses to control these conditions, they must continue with their normal regimen. However, subjects must have been utilizing these therapies for at least 30 days prior to Screening, no new regimens added during the course of the study, and no current regimens discontinued during the study.

- 5. Clinically significant conjunctivochalasis in either eye defined as an excessive redundancy of the conjunctiva that obliterates the inferior tear meniscus and/or rolls over the lower lid margin seen upon routine ocular exam or apparent with normal lid closure
- 6. Corneal conditions, other than dry eye related corneal epitheliopathies, affecting the corneal structure of either eye including but not limited to:
 - Clinically significant corneal dystrophies defined as affecting the structure of the corneal surface, affecting best-corrected visual acuity, or is an actively changing or unstable condition
 - Corneal scars with residual corneal surface irregularity
 - Pterygia that extend > 2mm onto the corneal surface, or are elevated rather than flat, or show concentrated staining
 - Keratoconus
- 7. Any history of ocular herpes simplex virus or herpes zoster virus infection, or other severe ocular conditions such as graft versus host disease, Stephen's Johnson Syndrome, sarcoidosis

- 8. Currently active, or history of ocular allergies during the time of year the subject will be participating in the study
- 9. History of hypersensitivity to ECF843, staining reagents (fluorescein sodium or lissamine), or their excipients.

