6.2.2 Prohibited medication

Use of the treatments displayed in the below table are not allowed after Screening (Visit 1).

Medication	Prohibition period	Action taken
Ocular, nasal, inhaled, or systemic corticosteroids	During the course of the study	Do not discontinue study treatment but document use of the product in the eCRF
Any topical ocular medications (prescription or over-the-counter; excluding IOP-lowering	During the course of the study	Do not discontinue study treatment but document use of the product in the eCRF
medication)		If the addition of a medication is needed for treatment of an adverse event, the decision to discontinue study treatment will be made by the Investigator and Sponsor based on the relevance and duration of the prohibited treatment
Intravitreal injections of any kind	During the course of the study	Do not discontinue study treatment, but document use of the product in the eCRF
		If the addition of a medication is needed for treatment of an adverse event, the decision to discontinue study treatment will be made by the Investigator and Sponsor based on the relevance and duration of the prohibited treatment
Medical device treatments such as those used to treat Meibomian gland dysfunction (eg, LipiFlow, pulse light therapy, etc)	During the course of the study	Discontinue study treatment
Punctal plugs or punctal cauterization	Placement of new occlusion during the course of the study	Discontinue study treatment

Table 6-2Prohibited medication

Subjects should be discouraged from using artificial tears, gels, lubricants during the study. However, if a subject is in need of occasional rescue and must use these products, the subject can remain in the study but the use of the products must be documented in the eCRF. If a subject is unable to refrain from use of these products and is unable to continue with the requirements of the study, the subject should be discontinued.

Topical ocular prescription medications should be administered at least 10 minutes before dosing with the study medication.

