Only subjects assigned exclusively to vehicle treatment in Part 1 may be eligible to participate in Part 2 of the study. A list of subjects eligible for screening in Part 2 of the study will be discussed between the Investigator and the Sponsor prior to initiating screening visits. In the event a study site was initiated close to the end of enrollment and did not have sufficient time to begin recruiting subjects in Part 1, the site may enroll subjects into Part 2 of the study if approved by the Sponsor.

Subjects are encouraged to stick to the scheduled visits as much as possible. If a subject is unable to return to the site as per the visit schedule, no visits should be missed, and efforts should be made to resupply the subject with sufficient drug (as needed). Subjects should be seen for all visits/assessments as outlined in the assessment schedule (Table 8-1 and Table 8-2) as close as possible to the target visit day and as close to the same time of day for each visit as possible. If a subject returns to the site for a visit earlier or later than planned, the next sequential visit should take place. The remaining subsequent visits should then be scheduled in a way that

brings the subject back to their original target dates for each visit as determined at Screening/Baseline.

Subjects must not have dosed with study medication within 4 hours of the visit assessments being conducted.

Missed or rescheduled visits should not lead to automatic discontinuation.

Subjects who prematurely discontinue the study for any reason should be scheduled for a visit as soon as possible, at which time all of the assessments listed for the final visit will be performed. At this final visit, all dispensed investigational product must be reconciled, and the adverse event and concomitant medications recorded on the eCRF.

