12.4.3 Handling of intercurrent events of primary estimand

The primary estimands will be the treatment effect of ECF843 against its corresponding vehicle, had subjects not taken artificial tears/gels/lubricants or prohibited medications as described in Section 6.2.2, and had they stayed on study treatment for the whole study duration. The hypothetical strategy assumes the subjects with intercurrent events (IEs) will behave like other subjects who did not take rescue/prohibited medications and stayed on study treatment. The primary analysis will account for different IEs as following:

- 1. Use of artificial tears/gels/lubricants: For subjects who use artificial tears/gels/lubricants occasionally for rescue, the data on the day(s) will be excluded and treated as missing.
- 2. Use of prohibited medications:
- For subjects who took ocular, nasal, inhaled, or systemic corticosteroids, intravitreal injections of any kind, the data on the day(s) + 3 days following the last day of prohibited medications will be excluded and treated as missing.
- For subjects who took the following prohibited medications,
 - Any topical ocular medications (prescription or over the counter; excluding IOP-lowering medication)
 - Medical device treatments such as those used to treat Meibomian gland dysfunction (eg, LipiFlow, pulse light therapy, etc)
 - Punctal plugs or punctal cauterization
- The data on the day(s) of prohibited medications will be excluded and treated as missing.
- 3. Discontinuation of study treatment for any reason: For subjects who discontinue study treatment, the data collected following the discontinuation will be excluded and treated as missing.

Missing data will be implicitly imputed under Missing at Random (MAR) assumption for MMRM analysis, that is missing data are imputed based on the treatment-specific information for the repeated measurements at baseline and post-baseline days/visits.

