# 2.7 Analysis of secondary efficacy objective(s)

#### 2.7.1 Secondary endpoints

The second efficacy objective is to evaluate the improvement of ECF843 vs vehicle in corneal damage by quadrant. The analysis of the secondary endpoints will be based on FAS 1.

•	Change from baseline in central corneal fluorescein staining
•	Change from baseline in inferior corneal fluorescein staining
•	Change from baseline in tear breakup time (TBUT)
•	Change from baseline in conjunctival lissamine staining score

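### Minor: the 4-hour gap before visit assessments covers study medication but not rescue lubricants, so sign exams whose rescue-day data are kept may follow recent lubricant use

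*Protocol*

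**What the plan says.** **Gap before visit exams.** Protocol Section 8 (Visit schedule and assessments) states: "Subjects must not have dosed with study medication within 4 hours of the visit assessments being conducted".

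**Gap for lubricants.** Protocol 5.2, exclusion criterion 2, reads: "Use of artificial tears, gels, lubricants within 4 hours of conducting assessments at the Screening Visit". The opening of 5.2 adds, for Part 2: "Subjects meeting any of the following exclusion criteria at the Screening and Baseline Visits in Part 2 are not eligible". Section 5 likewise applies the criteria at Part 2 Baseline.

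**Lubricants after screening.** Protocol 6.2.2 discourages them, but "if a subject is in need of occasional rescue and must use these products, the subject can remain in the study". Use must be recorded in the eCRF. No interval before a visit is given.

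**Analysis.** For the primary estimands, Protocol 12.4.3 says: "For subjects who use artificial tears/gels/lubricants occasionally for rescue, the data on the day(s) will be excluded and treated as missing". SAP Table 2-4 agrees. The supplementary estimand (Protocol 12.4.6, SAP Table 2-5) keeps all observed data. SAP 2.7.3 uses all observed data for the secondary endpoints, and SAP 2.13 uses observed data only for the exploratory endpoints. None of these last three states a rescue-day exclusion.

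**The concern.** The sponsor applies a 4-hour gap to lubricants at Screening and to study drops at visits. Only the remaining combination, lubricants at visits, has no stated gap.

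The protocol gives its own reasons to care. Section 2.1 justifies the primary estimands as capturing the drug effect "without confounding effects from prohibited medications or artificial tears/gels/lubricants". Section 4.1 says that "administration of vehicle does provide benefit to subjects and shows some efficacy in many dry eye clinical studies", so it accepts that a drop without the active ingredient can help. Rescue use is also foreseeable: inclusion criterion 5 selects people who regularly use these products or feel the need to.

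At stake is whether sign readings can be compared between visits and between arms in analyses that keep rescue-day data. That matters most for describing the secondary signs in Part 1 and for the search for areas of differentiation in Part 2.

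**Working it through.** The plan gives no figure on this point. Its only design calculation is the SANDE power, and the point does not depend on it. As a check, with 112 per arm, difference 10 mm, SD 23 mm and alpha 0.05/3:

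- standard error = 23 × √(2/112) = 3.07
- 10/3.07 = 3.25, against a critical value of 2.39
- power = 80.5% (79.9% with the noncentral t), against the stated 80%

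A lubricant gap changes none of this.

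**Step 1. Does the Section 8 rule already cover lubricants?** No. Protocol 6.1.2 limits trial treatment to investigational and control drug. The glossary lets study treatment include non-investigational products, but only those given as part of required procedures. A self-chosen rescue tear is not that. The 10-minute rule in 6.2.2 concerns prescription drops before dosing, not lubricants before an exam.

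**Step 2. Set the rules side by side.**

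| Product | Screening | Later visits |
|---|---|---|
| Study medication, including vehicle | not yet dispensed | 4 hours (Section 8) |
| Artificial tears, gels, lubricants | 4 hours (exclusion 2) | none stated |

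Followed exactly, a vehicle drop 3 hours before an exam breaks the rule, and an artificial tear 10 minutes before it does not.

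Part 2 Baseline is a wording ambiguity. The opening of 5.2 brings it in, while criterion 2 names Screening only.

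**Step 3. Does the analysis close the gap?**

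| Analysis of signs | Data from a rescue day |
|---|---|
| Primary, composite corneal staining | deleted |
| Supplementary estimand, composite staining | kept by design |
| Secondary signs | kept (all observed data) |
| Exploratory signs, including Part 2 | kept (observed data) |

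For same-day use, deleting the whole day is stricter than a 4-hour gap, so the primary analysis is covered after baseline. Part 1 baseline cannot be judged because the definition in SAP 2.1.1.3 is partly redacted.

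SAP 2.7.1 also lists TBUT and lissamine staining, while SAP Table 1-2 and 2.7.2 name only central and inferior staining. Whether those two are secondary or exploratory, no rescue-day exclusion is stated.

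**Step 4. What form would a bias take?** Suppose fractions pV (vehicle) and pT (ECF843) use a lubricant shortly before the exam, and each use shifts the reading by s. The shift in the between-arm difference is (pV − pT) × s in size. The fractions below are assumptions, because the documents give none.

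| pV | pT | Shift in difference |
|---|---|---|
| 5% | 5% | 0 |
| 10% | 5% | 0.05 s |
| 20% | 10% | 0.10 s |
| 30% | 10% | 0.20 s |

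Equal use leaves the difference unbiased, though each arm's own mean moves by p × s (0.05 s at 5%). Higher use on vehicle works against ECF843 if lubricants transiently improve signs. Since s is unknown, no effect size follows.

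**The case against.** **The absence claim is limited by missing text.** Footnotes 1 and 2 of Table 8-1 and nearly all notes to Table 8-2 are missing from the public copy, as are Protocol 12.6 and SAP 2.12, where exploratory and Part 2 methods might sit. Any of these could hold a lubricant instruction or a rescue-day exclusion. This stands, and the point is confined to the visible text.

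**Existing controls are real.** Lubricants are discouraged, allowed only as occasional rescue, and recorded. A subject who cannot refrain and cannot meet study requirements should be discontinued. SAP 2.4.2.1 summarises rescue users by arm, and the SAP 2.4.2 listings carry medication dates, so a same-day exclusion could be run as a check. This also stands, and it makes a new time-of-use field optional.

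**Using all observed data for descriptive endpoints is legitimate,** as is the supplementary estimand's deliberate retention of rescue-day data. Agreed. The point concerns standardising the measurement, not the estimand.

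**A reader might infer that TBUT and lissamine staining are the clear cases,** because their schedule rows carry no footnote mark and corneal staining does. The documents do not support that distinction. The exams share one sitting: Protocol 8.3.3 lets corneal staining use the dye already instilled for TBUT, and 8.3.4 places lissamine after corneal staining. A gap attached to corneal staining would cover all three.

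**Conclusion.** The gap holds on the visible text and is minor. The stated rule, followed exactly, admits post-baseline exams soon after a product that the protocol itself treats as a confounder. The affected analyses are the secondary and exploratory signs and the supplementary estimand.

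No effect size can be given. The secondary endpoints have no hypothesis test (SAP 2.7.2) and no power considerations (Protocol 12.8.2), and Part 2 is exploratory (SAP 1.1.2).

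Two stronger readings are not supported. A reader might infer that the primary staining result is confounded, but same-day deletion protects it after baseline. A reader might also multiply scheduled exams by subjects to get a magnitude. That would count exams the rule would cover, not exams affected, and would count exams from one sitting more than once.

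The conclusion assumes that the missing footnotes and sections contain no further lubricant instruction or exclusion. Any directional bias also requires unequal use between arms and a transient lubricant effect, neither of which the documents establish.

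**What to change.** In the Section 8 sentence, insert *or used artificial tears/gels/lubricants* after *study medication*, so that one 4-hour rule applies at every visit. Reword exclusion criterion 2 so that it plainly covers the Part 2 Baseline Visit as well as Screening. Leave the rescue policy and the handling of intercurrent events unchanged.

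An eCRF field for the time of last lubricant use is optional. It would identify exams inside the 4 hours, which dates alone cannot do, but the medication dates already allow a same-day check.

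The cost is a few words, plus occasional waiting or rescheduling. That may move an exam away from the consistent time of day that Section 8 also asks for. Four hours is the sponsor's own interval; the documents do not show whether it is long enough for gels.

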8.1 Screening

No subjects may be re-screened if they fail entry criteria for any reason other than required stabilization time frames for medications and/or medical history.

If a subject is enrolled and it is determined prior to the completion of Visit 1 that the subject did not meet criteria pertaining to:

- duration of DED diagnosis;
- time frame required for stabilization of chronic medications or therapies, time frames related to medical history or use of contact lenses

the subject will be screen failed and brought back at a later date to re-attempt the screening process once the proper time frames have been achieved.

In the case of re-screening, the subject will receive a new subject number and all screening assessments required at Visit 1 must be completed on the day of randomization, regardless if the assessments were conducted at the previous screening visit.

Re-screening is only allowed one time for a particular subject and per part of the study. Rescreening must not be used as a method to force subject eligibility into the study.

For subjects requiring washout of prior medications or contact lenses, informed consent must be obtained prior to washout. Subject will be enrolled into the study and brought back for screening assessments (Visit 1) after the washout is completed.

8.1.1 Information to be collected on screening failures

Subjects who sign an ICF and subsequently found to be ineligible prior to randomization will be considered a screen failure. The reason for screen failure should be recorded on the appropriate eCRF. The demographic information, informed consent, and Inclusion/Exclusion pages must also be completed for screen failure subjects. No other data will be entered into the clinical database for subjects who are screen failures, unless the subject experienced a serious adverse event during the screening phase (see Section 10.1.3 for SAE reporting details). If the subject fails to be randomized, the IRT must be notified within 2 days of the screen fail and that the subject was not randomized.

Subjects who are randomized and fail to start treatment, e.g. subjects randomized in error, will be considered an early terminator. The reason for early termination should be recorded on the appropriate eCRF.

